#### 4.1.2. Secondary outcomes

i) Biochemically verified 7-month continuous abstinence from tobacco smoking (dichotomous: abstinent or not)

- Self-reported 7-month continuous abstinence at 9-month survey will be verified using measures of CO in expired air. A cut-off point of 8ppm will be used to define a smoker (i.e. CO level <8ppm will be considered biochemically verified abstinent).

ii) 30-day point prevalence abstinence (PPA)

- Two items will be used to assess self-reported 30-day PPA: "Have you smoked at all, even a puff, in the last 30 days?" (response options: yes; **no**), and "How many cigarettes have you smoked in the last 30 days?" (response options: **less than 1 or just a puff**; 1 – 5; 6 – 10; 11 – 20; more than 20).

Participants who report not having smoked in the last 30 days AND smoking 'less than 1' cigarette or 'just a puff' in last 30-days will meet 30-day PPA criteria.

iii) 7-day PPA

- Self-reported 7-day PPA will be measured by asking participants "Have you smoked at all, even a puff, in the last 7 days?" with response options a) yes, b) no. Responding 'no' will equate to self-reported 7-day PPA.

iv) Number of cigarettes smoked and percentage reduction from baseline (dichotomised: at least 50% or < 50%)

- Participants will be asked "currently how many cigarettes do you smoke per day, per week, and per month?".
- Only asked of participants who report that they are occasional/ daily smoking (if the participant reports quitting in the primary outcome they are excluded from this analysis)
- Percentage reduction in number of cigarettes smoked from baseline (dichotomised: at least 50% or < 50%)
- Reduction rate also to be calculated

v) Reducing cravings to smoke

- Frequency of cravings was assessed by one item^3: "How often do you get cravings to smoke tobacco?" with response options: a) hourly or more often, b) several times per day, c) at least once a day, d) less than daily, or e) never.

vi) Reducing withdrawal symptoms (24 hours, 30 days)

- 24 hours (measured at baseline and 3 months)

Nicotine withdrawal symptoms over past 24hours was measured at baseline and 3-month follow-up using the Minnesota Nicotine Withdrawal Scale (MNWS), with symptoms [angry, irritable frustrated; anxious or nervous; depressed or sad; desire or craving to smoke; difficulty concentrating; increased appetite, hungry or weight gain; insomnia, sleep problems or awakening at night; restless or impatient] experienced in last 24 hours rated on an ordinal scale ranging from 0 (none), 1 (mild), 2 (moderate), to 3 (severe).

- Last 30 days (past week assessed at baseline; last 30 days at 3-month and 9-month follow-up)

A modified version of the MNWS was used to assess withdrawal symptoms over past 30 days. At baseline participants were asked "In the week before you came here, how often were you bothered by the following problems", and at 3-month and 9-month

follow-up timepoints “In the last 30 days, how often were you bothered by the following problems?” and asked to rate the list of withdrawal symptoms from 0 (not at all), 1 (several days), 2 (more than half the days), to 3 (nearly every day).

vii) Relapse episodes

- **Instance of relapse at 3-month follow-up** will be determined by:  
Answering ‘daily’ or ‘yes, at least once a week’ to question of “*do you currently smoke any tobacco products*”  
OR  
Answering ‘less often than once a week’ or ‘not at all’ to current smoking status **AND** answering ‘yes’ to question “*since you left service, have you smoked every day for a week or more?*”
- **Time to relapse at 3-month follow-up** is assessed by the question “How soon after discharge did you go back to smoking (your first smoke after discharge)?” with response options a) as soon as I could get a cigarette that day; b) later on the day I got out; c) on the day after I got out; d) 2-7 days after I got out; e) more than a week after I got out but less than 1 month; f) more than a month after I got out.
- **Instance of relapse at 9-month follow-up** is determined by:  
Answering ‘not at all’ to *current smoking status* **AND** responding ‘yes’ to question “*Since you quit smoking, have you smoked every day for a week or more (even just puffs)? (yes/no)*”  
OR  
Current (daily or occasional) smokers who report a quit attempt within past 6 months that lasted  $\geq 2$  days

vii) Abstinence from all nicotine/ tobacco products

- This will be measured by asking participants "Are you currently using any form of nicotine products, including vapourised nicotine products and tobacco products other than cigarettes? Check all that apply" with response options a) no; b) yes, nicotine patches; c) yes, oral nicotine products; d) yes, nicotine vaping products; e) yes, some other form of tobacco product. Responding ‘no’ will equate to ‘Abstinence from all nicotine/ tobacco products.’

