#### **2.2.2. Secondary objectives**

Additional secondary objectives are to compare participants in the VNP + Quitline to those in the NRT + Quitline group on:

- i) Biochemically verified 7-month continuous abstinence at month 9
- ii) 30-day point prevalence abstinence at months 3 and 9
- iii) Reduction in cigarettes smoked per day at months 3 and 9
- iv) Reduction in strength and urges to smoke tobacco at months 3 and 9
- v) Reduction in withdrawal symptoms at months 3 and 9
- vi) Relapse episodes to smoking at months 3 and 9

Other objectives involve:

- i) Assessing treatment adherence (duration/ use of products/ reasons for non-use/ engagement with telephone counselling) compared by treatment group
- ii) Assess attitudes/ acceptability of the provided interventions
- iii) Use of additional pharmacotherapies, visits to GPs, and use of print and online materials
- iv) Assess provided interventions on mood

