#### 4.1.5. Analysis populations

The primary analysis population will be the intention to treat (ITT) population, defined as all participants that were randomised to an intervention arm. Participants

that drop out of the study will have their outcomes imputed using the methods described in the “missing data section”.

Secondary analysis population will include the 1) completers, defined as all participants that were randomised to receive an intervention, and returned for a follow-up survey with complete data (i.e., complete case analysis); 2) the intention to treat population, Participants that drop out of the study will have their outcomes imputed using the methods described in the “missing data section”. 3) the per protocol analysis excluded participants with major protocol violations (e.g. death, pregnancy, study withdrawal, loss to follow-up, non-adherence, non-compliance). Self-reported adherence was defined as having been sent all 12 weeks’ study medication from the study team AND a quitline referral. Self-reported medication compliance was defined as current or previous use of NRT (use of patches for  $\geq 7$  weeks AND any oral form use) or VNP (use for  $\geq 7$  weeks) according to group assignment.

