#### 4.3.2. Secondary outcome models

Secondary abstinence outcomes will be assessed in the ITT population, other secondary outcomes in the completers and the ITT population. GLMM will be used to assess the difference in outcomes at follow up between treatment groups or changes from baseline.

All single endpoint outcomes will include a normally distributed random intercept for site (on the scale of the canonical link function for the specific distribution family) and treatment group as a fixed effect with a non informative prior for the treatment effect. The random intercept will be modelled from a normal distribution with mean 0 and a hierarchical variance parameter that is distributed as a half Student-T of 3 degrees of freedom.

For outcomes with multiple time points, the models will additionally include participant id as a random intercept, and parameters for time with an interaction between time and treatment group as fixed effects, all on the scale of the canonical link function for the specific distribution family. Non-informative priors will be used for fixed effects. Participant id

random intercept will be modelled from a multivariate normal distribution with mean 0 and covariance matrix with a non-informative prior (LKJ-Correlation and half Cauchy priors implemented in the brms R package).

A GLMM with a binomial distribution and logit link function will be used to model abstinence outcomes (biochemically verified 7-month continuous abstinence, self-reported 30 day and 7 day point prevalence, abstinence at 3 and 9 months).

Number of cigarettes smoked per day will be compared at each time point using a GLMM with a negative-binomial distribution and log link function. Percentage reduction of at least 50% in the number of cigarettes smoked per day will be assessed with GLMM with a binomial distribution and logit link function.

Craving scores and relapse episodes will be compared using a GLMM with multinomial distribution and a cumulative logit link function, or binomial distribution and logit link depending on the distribution of responses.

Withdrawal scores will be compared using a GLMM with normal distribution and identity link function.

Abstinence from all nicotine/ tobacco products will be modelled using GLMM with a binomial distribution and logit link function.

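### The cigarettes-per-day and 50%-reduction comparisons leave out participants who quit, although the SAP assigns these outcomes to all randomised participants

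*SAP*

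**What the plan says.** Section 2.2.2 lists a between-arm objective: "Reduction in cigarettes smoked per day at months 3 and 9". Section 4.1.2(iv) derives two outcomes from one survey item: the number of cigarettes smoked, and whether it has fallen by at least 50% from baseline. On who contributes, it says "Only asked of participants who report that they are occasional/ daily smoking", and then that "if the participant reports quitting in the primary outcome they are excluded from this analysis".

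Section 4.3.2 plans treatment comparisons for both outcomes: "Number of cigarettes smoked per day will be compared at each time point using a GLMM with a negative-binomial distribution and log link function", and "Percentage reduction of at least 50% in the number of cigarettes smoked per day will be assessed with GLMM with a binomial distribution". It places them in "other secondary outcomes in the completers and the ITT population". Section 4.1.5 gives the ITT population as "defined as all participants that were randomised to an intervention arm".

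Section 4.1.1 defines the primary outcome at month 9 only: not smoking at all now, and last daily smoking at least 7 months ago. Section 4.5 treats missing abstinence as not abstinent in the main analysis and uses multiple imputation with predictive mean matching as a sensitivity analysis.

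**The concern.** The exclusion selects participants on something that happens after randomisation and that the trial expects treatment to change. Once quitters are removed, the arms are those who failed to quit on VNP and those who failed to quit on NRT. These are no longer groups formed by randomisation.

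Those removed also have the largest possible reduction, 100%, and so satisfy the at-least-50% criterion by definition. If VNP works as planned, more of them come from the VNP arm. Section 2.1 gives harm reduction as part of the rationale for VNPs, and this is the outcome that measures it. Reported under an ITT label, the result could be taken for the randomised effect on reduction when it is not.

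**Working it through.** **1. How non-smokers leave the analysis.** There are two routes, and the SAP does not separate them.
- *The stated exclusion.* Read literally with Section 4.1.1, it covers only participants who meet 7-month abstinence at month 9.
- *The skip rule.* Someone who answers *not at all* but quit more recently is not excluded by that sentence. They are also not asked the item, so they have no value. No section says whether they are excluded, missing or zero. If treated as missing, predictive mean matching would fill the gap from observed answers, all of which come from people who smoke.

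At month 3 the primary outcome does not yet exist, so how the exclusion applies there is unclear.

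**2. The SAP's own planning figure (Section 3.4).** Inputs: 3% v 9%, two-sided 5%, 80% power, 40% attrition.
- n = [1.96√(2 × 0.06 × 0.94) + 0.8416√(0.03 × 0.97 + 0.09 × 0.91)]² / 0.06² = 245 per group. With the continuity correction it is 278, as stated.
- 2 × 278 / 0.60 = 926.7, against 926 stated.

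The planning rates therefore reproduce. No figure is given for the reduction outcome.

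**3. How many the stated exclusion removes.** With 926 / 2 = 463 per arm: 463 × 0.03 = 14 NRT and 463 × 0.09 = 42 VNP. With the 278 per arm left after attrition: 8 and 25. Either way, three times as many leave from VNP.

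**4. At-least-50% reduction.** Let q be the quit rate and r the share of continuing smokers who halve consumption. The SAP does not give r; I assume it is equal in both arms and vary it.
- Quitters excluded: the proportion is r in each arm, so the odds ratio is 1.00 whatever r is.
- Quitters counted: the proportion is q + (1 − q)r. At r = 40%, VNP is 0.09 + 0.91 × 0.40 = 0.454 and NRT is 0.03 + 0.97 × 0.40 = 0.418.

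| r (assumed) | VNP | NRT | OR, quitters counted | OR, quitters excluded |
|---|---|---|---|---|
| 20% | 27.2% | 22.4% | 1.29 | 1.00 |
| 30% | 36.3% | 32.1% | 1.21 | 1.00 |
| 40% | 45.4% | 41.8% | 1.16 | 1.00 |
| 50% | 54.5% | 51.5% | 1.13 | 1.00 |

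**5. Mean cigarettes per day.** Assume continuing smokers have the same mean m in both arms. With quitters excluded, the VNP/NRT ratio is m/m = 1.00. With quitters at zero it is 0.91m / 0.97m = 0.94.

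**The case against.** **It may be a choice of estimand.** Reduction among continuing smokers is a recognisable question, the restriction is stated openly, and the objective in Section 2.2.2 does not say that quitters are included. This stands in part: such a summary is legitimate if labelled. It does not reconcile the exclusion with the ITT population named for the same outcome, or make the comparison a randomised one.

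**The consequences are small.** This stands. Under equal r, the gap is the 6-point quit effect times (1 − r), for example 0.06 × 0.60 = 3.6 points at r = 40%. The abstinence outcomes already report that effect. Taking a two-sided 5% test as a yardstick, power for 45.4% v 41.8% is about 14% with 278 per arm and 20% with 463, so including quitters would seldom change the conclusion at the planned rates.

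A reader might infer three stronger claims, none of which the SAP supports:
- *That everyone who quit is excluded by rule.* The sentence reaches only those who meet the primary outcome. Other non-smokers are lost through the skip rule, and their status is undefined.
- *That the month-3 comparison is selected on a month-9 result.* The SAP does not say so. Because the item goes to current smokers, a survey-by-survey reading is at least as natural.
- *That the exclusion reverses the direction of effect.* It can under added assumptions. If lighter smokers quit more readily (−0.08 log-odds per cigarette, mean 20 per day), the smokers-only means are 14.14 v 14.05, a ratio of 1.007. That is a 0.7% difference resting on a slope the SAP does not give; with no slope the ratio is 1.00. Likewise, if all the extra VNP quitters would otherwise have halved consumption, the smokers-only odds ratio falls to 0.69 (r = 20%) or 0.88 (r = 50%), but the SAP gives no information on who quits. The supportable statement is that an effect can appear as none.

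**Conclusion.** The point holds. Section 4.1.2(iv) conflicts with Sections 4.1.5 and 4.3.2, and non-smokers have neither a zero rule nor a clear status, at month 3 in particular. Followed as written, the plan makes a treatment comparison conditional on a post-randomisation outcome and omits participants with a 100% reduction.

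The sizes in the table, and the shift in mean ratio from about 1.00 to about 0.94, rest on the SAP's 9% v 3% and on the assumption that continuing smokers behave alike in the two arms. The bias is modest and affects one of the eight listed secondary outcomes. The primary analysis and the sample size are untouched. It should be corrected before analysis, but it does not threaten the trial's main conclusion.

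**What to change.** - **Recode.** At each survey, set cigarettes per day to 0 and percentage reduction to 100% (at least 50% = yes) for anyone answering *not at all* to the current-smoking item at that survey. Remove the reference to the primary outcome, which also settles month 3.
- **Population.** Include everyone with follow-up in the completers analysis and everyone randomised in the ITT analysis.
- **Missing values.** For those lost to follow-up, use the SAP's multiple imputation, run after the recode so that known non-smokers are not imputed positive counts. Counting missing participants as not abstinent supplies no cigarette count, so the SAP must name the method here.
- **Model.** The negative binomial accepts zeros. Use a hurdle or zero-inflated version if the posterior predictive check in Section 4.2.5 shows poor fit.
- **Label.** Present any smokers-only comparison as descriptive and non-randomised.

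The cost is a few lines of SAP wording, one recode and possibly a different count model. No new data are needed, because current smoking status is already collected.

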#### **4.5. Missing Data**

It is anticipated that there will be two main mechanisms that will enable missing data will be observed in the data sources for the primary and secondary outcome: 1) participant that have not completed the follow-up CATI surveys (at 3 or 9-months) and are considered lost to

follow-up; and 2) participants that were successfully reached at follow-up; however, the outcome is missing. It is expected the first scenario is most likely.

The main analysis will be conducted in the intention to treat population. The primary method of imputing missing data will follow the recommendations of the Russel Standard, and assume those with missing data to be not abstinent.

A sensitivity analysis will be conducted under the missing at random assumption and, if evidence of a treatment effect is shown then missing not at random (MNAR). The analysis will be conducted using multiple imputation by chained equations with predictive mean matching models (PMM). PMM models will use analysis variables (treatment, site, time and outcomes) plus variables known to be predictors of abstinence (???) and any variables found to be predictive of missingness. Chisq or t-tests on baseline psychometrics will be used to assess association with missingness on the primary outcome to include in the PMM models. The number of imputations will be the higher of the percentage missing or 25 and 20 iterations will be used. The stability of the results will be explored through increasing the number of imputations. Pattern mixture models will be used to assess the sensitivity of the missing at random assumption. A tipping point approach will be used by varying our assumptions regarding the outcome proportion for those with missing data in the treatment group until a positive treatment effect is nullified. This sensitivity analysis will enable a better understanding of the variability of the missing data and will be used to assess the impact of missing on the outcomes of the study.

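### The 3-month time-to-relapse item times the first smoke, not the SAP's relapse event, and has no value for participants who have not smoked, so a comparison of arms covers only those who resumed

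*SAP*

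**What the plan says.** Section 2.2.2 lists "Relapse episodes to smoking at months 3 and 9" as a secondary objective. Section 4.1.2 gives that outcome three parts: instance of relapse at 3 months, time to relapse at 3 months, and instance of relapse at 9 months.

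- **Time to relapse** comes from one question: "How soon after discharge did you go back to smoking (your first smoke after discharge". It has six answers, a to f, starting with the day of discharge and ending "e) more than a week after I got out but less than 1 month; f) more than a month after I got out". There is no answer for someone who has not smoked, no censoring rule and no statement of who is asked.
- **Instance of relapse at 3 months** needs current daily or at least weekly smoking. Those smoking less often or not at all count only if they answer yes to "since you left service, have you smoked every day for a week or more".
- **Model** (4.3.2): "Craving scores and relapse episodes will be compared using a GLMM with multinomial distribution and a cumulative logit link function", or a binomial logit, depending on the distribution of responses. Time to relapse is not named separately and no time-to-event method is given.
- **Populations** (4.3.2): "other secondary outcomes in the completers and the ITT population". Section 4.1.5 defines completers as those who "returned for a follow-up survey with complete data (i.e., complete case analysis".
- **Missing data** (4.5): the main rule is to "assume those with missing data to be not abstinent", with multiple imputation under missing at random as a sensitivity analysis. Neither is spelled out for this item.

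**The concern.** There are two defects.

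First, the label and the measurement refer to different events. A participant who smokes once on the day of discharge and never again has the shortest possible time to relapse, yet has not relapsed under the rule beside it.

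Second, the best result, no smoking since discharge, has no place on the scale. A complete-case ordinal model therefore compares only those who smoked. Treatment influences who is in that group, so randomisation no longer protects the comparison. An arm that keeps people smoke-free gets no credit for it here. If those people would otherwise have lapsed late, the arm also loses its later answers.

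The omission does not follow a convention of the SAP. The craving item in 4.1.2 includes a never option, and the cigarettes item states who is asked and who is excluded.

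**Working it through.** **No SAP figure to reproduce.** The SAP gives no expected distribution for this item. From section 3.4 I borrow only the 3% (NRT) and 9% (VNP) abstinence rates and, for precision, the 278 followed per arm. These are 9-month figures, so using them at 3 months is an assumption. All timing distributions and other abstinence shares below are also assumptions.

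**Method.** A two-arm cumulative-logit model, logit P(Y > k) = c_k + b × VNP, is fitted to expected category proportions without a site effect. OR = exp(b), and OR > 1 means later or no first smoke on VNP. Each fit is done with no smoking as a seventh, highest category, and again with abstainers dropped.

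**Illustration 1: assumed timing among control smokers of 35/15/15/15/12/8% over a to f.** Two cases are considered:

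- Case A: timing among those who smoke is the same in both arms; only the abstinent share differs.
- Case B: the extra VNP abstainers come from the latest lapsers (f first, then e).

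For 3% against 9% abstinent, per 100 followed (control a = 0.97 × 35 = 33.95; Case A a = 0.91 × 35 = 31.85; Case B f = 7.76 − 6 = 1.76):

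| | a | b | c | d | e | f | none |
|---|---|---|---|---|---|---|---|
| Control | 33.95 | 14.55 | 14.55 | 14.55 | 11.64 | 7.76 | 3 |
| VNP, A | 31.85 | 13.65 | 13.65 | 13.65 | 10.92 | 7.28 | 9 |
| VNP, B | 33.95 | 14.55 | 14.55 | 14.55 | 11.64 | 1.76 | 9 |

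One cut of Case B shows the mechanism. With everyone included, f or later is 7.76 + 3 = 10.76 in control and 1.76 + 9 = 10.76 on VNP, so there is no difference at that cut. Among smokers only, f is 7.76/97 = 8.0% against 1.76/91 = 1.9%, which looks like earlier smoking on VNP although nobody smoked sooner.

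Fitted ORs:

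| Abstinent, NRT vs VNP | A: kept | A: dropped | B: kept | B: dropped |
|---|---|---|---|---|
| 3% vs 9% | 1.21 | 1.00 | 1.02 | 0.82 |
| 5% vs 15% | 1.37 | 1.00 | 1.06 | 0.72 |
| 15% vs 30% | 1.60 | 1.00 | 1.16 | 0.57 |

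With 278 followed per arm, approximate 95% intervals for the 5% vs 15% row are:

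- Case A: 1.37 (1.02 to 1.84) kept, 1.00 (0.73 to 1.37) dropped.
- Case B: 1.06 (0.79 to 1.42) kept, 0.72 (0.53 to 0.99) dropped.

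**Illustration 2: Weibull time to first smoke, shape 0.4.** Control survival is S0(t) = s^((t/91)^0.4), where s is the share smoke-free at 91 days, with category limits at 0.25, 1, 2, 7, 30 and 91 days.

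- Hazard ratio 0.6, so S1 = S0^0.6. The VNP smoke-free share is 0.10^0.6 = 25.1% or 0.15^0.6 = 32.0%. For s = 10%, OR is 2.12 kept and 1.51 dropped; for s = 15%, 2.09 and 1.42.
- Ten percentage points moved from e and f (in proportion) to no smoking, all else unchanged. For s = 10%, OR is 1.14 kept and 0.78 dropped; for s = 15%, 1.17 and 0.79.

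**Reading.** Dropping abstainers dilutes a general delay, removes a benefit that lies only in abstinence, and reverses the sign when late lapsers are the ones converted.

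**The case against.** - **A reader might infer that the trial discards its relapse-prevention benefit.** It does not. The 3-month instance of relapse covers everyone followed and counts an abstainer as not relapsed. The 7-day and 30-day abstinence outcomes and the primary outcome also capture the benefit.
- **A reader might infer that abstainers will be imputed as relapsers.** The SAP does not say so for this item. Section 4.5 concerns participants lost to follow-up, or reached but with the outcome missing, and a not-applicable blank need not be either. If such blanks were treated as missing, predictive mean matching could only supply one of the six smoking times, and the not-abstinent rule has no defined value on this scale. That is a reason to exclude them explicitly, not evidence of a stated rule.
- **Reversal is a special case.** With a hazard ratio of 0.6 the direction is kept, and with equal timing among smokers the result is null. This objection stands.
- **The model is partly inferred.** Section 4.3.2 names relapse episodes, not time to relapse. However, the two instance-of-relapse measures are binary, so this six-level item is the natural target of the cumulative logit.
- **The questionnaire may route abstainers past the item.** They would still have no value. A description among those who resumed smoking is legitimate; the fault lies in using it to compare randomised arms.
- **The label is disclosed in the question itself.** True, but it still conflicts with the adjacent definition.

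**Conclusion.** The point holds at moderate severity. Two elements rest on the text alone: the item times a different event from the SAP's relapse, and it has no value for participants who have not smoked. Applying the complete-case definition and a logit model then restricts the arm comparison to a group selected after randomisation.

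The size cannot be fixed from the SAP. Under the assumed inputs, an OR of about 2.1 shrinks to 1.4 to 1.5, and one of 1.21 to 1.60 becomes 1.00. If mainly late lapsers become abstainers, 1.02 to 1.17 becomes 0.57 to 0.82. The documents do not support a claim that reversal is expected. Only this one part of a secondary outcome is affected.

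**What to change.** 1. Rename the outcome time to first smoke after discharge, so that it no longer competes with the relapse definition.
2. Analyse all participants followed at 3 months with seven ordered categories, the highest being no smoking reported since discharge. Alternatively, treat it as interval-censored time, censored at the survey.
3. Assign the top category to those who completed the 3-month survey, left this item blank, and report not smoking at all currently, no smoking in the last 30 days and no week of daily smoking since leaving.
4. State that their blank is not applicable and is not imputed.

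The cost is SAP wording and a recode of the 3-month data, with one downside to state. The 7-day and 30-day items do not reach back to discharge, and the week-of-daily-smoking item misses isolated smoking. Without an explicit answer for not having smoked, or a known skip pattern, a few people with brief early smoking who left the item blank could be misclassified. If the category cannot be identified, report the item descriptively among those who resumed smoking and draw no between-arm inference from it.

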## 4. ANALYSIS

### 4.1. Outcome Definitions

#### 4.1.1. Primary outcome

Self-reported 7-month continuous abstinence (dichotomous: abstinent or not) at 9 months post randomization

Self-reported 7-month continuous abstinence will be assessed using the following items:

- “Do you currently smoke any tobacco products?” (response options: yes daily; yes, at least once a week; yes, less often than once a week; **no, not at all**)
- “How long ago did you last smoke every day?” (response options: Less than 1 week; 1 week to 1 month; 1 – 3 months; 4 – 6 months; **7 – 9 months; more than 9 months**) reporting either “7-9 months”, “or more than 9-months”.

Participants that report they are currently ‘not smoking at all’ AND that it has been either ‘7-9 months’ or ‘more than 9 months’ since they last smoked every day are considered to have reached 7-months continuous abstinence.

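### At month 9, relapse in current non-smokers rests on one item whose starting point is undefined, so some who relapsed after month 3 and re-quit can be scored as not relapsed against the same survey's own data

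*SAP*

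**What the plan says.** SAP 2.2.2 lists as a between-arm comparison "Relapse episodes to smoking at months 3 and 9", and 4.3.2 gives its analysis: "Craving scores and relapse episodes will be compared using a GLMM". Section 4.1.2 vii sets a separate scoring rule for each time point.

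- **Month 3.** Daily or at-least-weekly smokers are relapses. Anyone smoking less often, or not at all, is a relapse on answering yes to "since you left service, have you smoked every day for a week or more".
- **Month 9, not smoking.** There is one route to relapse, a yes to "Since you quit smoking, have you smoked every day for a week or more (even just puffs)? (yes/no".
- **Month 9, smoking.** The route is different: "Current (daily or occasional) smokers who report a quit attempt within past 6 months that lasted" two days or more.

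For the primary outcome, 4.1.1 also uses the question "How long ago did you last smoke every day", with six answer bands. Only the top two (7–9 months and more than 9 months) are compatible with continuous abstinence. The month-9 relapse rule uses neither this answer nor the participant's month-3 relapse status.

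**The concern.** The month-3 look-back starts at discharge, an event that everyone shares. The month-9 look-back for non-smokers starts at the participant's own quit, which is neither dated nor defined. A person who went back to daily smoking and stopped again has at least two candidate quits. Counting from the latest, the truthful answer is no; counting from the one at the facility, it is yes. The score therefore depends on how each respondent hears the question.

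At stake is the month-9 half of secondary objective vi. Those whom the item can miss are by definition successful re-quitters, and in both arms Quitline calls are to be more frequent around relapse (3.2.1, 3.2.2). If re-quitting differs between arms, the arm with more of it can appear to have fewer relapses. If the two time points are modelled together, the change of starting point also enters the time and time-by-treatment terms.

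**Working it through.** The SAP states no figure for this outcome, so the check is to run the rules on example histories. Each person is not smoking at month 9. Months count from discharge, and time since last daily smoking is 9 minus the month in which it ended.

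| History | Month-3 score | Month-9 item, latest quit | Month-9 item, quit at facility | Last daily smoking | Primary outcome |
|---|---|---|---|---|---|
| A. No smoking since admission | No relapse | No relapse | No relapse | Top band | Abstinent |
| B. Abstinent to month 4, daily in months 4–5, re-quit | No relapse | **No relapse** | Relapse | 9 − 5 = 4 months: 4–6 band | Fails |
| C. Daily from discharge to month 4, re-quit | Relapse, if surveyed | **No relapse** | Relapse | 9 − 4 = 5 months: 4–6 band | Fails |
| D. Daily for the first month, re-quit | Relapse, if surveyed | **No relapse** | Relapse | 9 − 1 = 8 months: 7–9 band | Abstinent |

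- **B** is the clear failure. Under the latest-quit reading no rule at either time point records the relapse, although the month-9 survey shows daily smoking after month 3.
- **C** is recorded as a relapse at month 3. It is lost altogether only if the 3-month survey was missed.
- **D** is likewise caught at month 3 if surveyed. The last-daily-smoking item cannot recover it, because the 7–9 band does not separate a relapse that ended early from smoking before admission.

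The current-smoker route cannot rescue B, C or D, since none of them smokes at month 9.

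**Possible size.** Let c be the share of an arm that never relapsed and r the share that relapsed and re-quit by month 9. Re-quitters as a share of month-9 non-smokers are r/(c + r). For illustration, c runs over the 3% and 9% continuous-abstinence rates assumed in 3.4, and r is assumed to span the same range:

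- c = 9%, r = 3%: 3/12 = 25%
- c = 3%, r = 3%: 3/6 = 50%
- c = 9%, r = 9%: 9/18 = 50%
- c = 3%, r = 9%: 9/12 = 75%

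The range is 25% to 75%. It bounds the share missed from above, because it includes people caught at month 3 and people who answer from the quit at the facility.

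**The case against.** The best defence is that the SAP nowhere says that the item looks back to the latest quit. Counted from the quit at the facility, it works. There is even a reason to think that this was meant: under the latest-quit reading a current non-smoker could hardly answer yes, because a week of daily smoking would normally end that quit and begin another. This stands as far as it goes. A reader might infer that the item certainly misses re-quitters, and the document supports only that it can. But the plan leaves the starting point open where the month-3 item fixes it, and it holds the data to settle the matter without using them.

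Three further inferences also go too far.

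- **That anyone who resumed smoking at discharge and later re-quit is recorded as never having relapsed.** History C shows otherwise: the month-3 rule records the relapse if that survey was done.
- **That month-9 relapse must be cumulative since discharge.** The SAP does not say so. The current-smoker route looks back six months, roughly the interval since month 3, so an interval outcome may be intended. History B is missed under either window.
- **That the bias can be expressed as an odds ratio.** It cannot be from this document. Current smokers are scored by the separate quit-attempt rule, and the SAP gives no rates for them or for re-quitting.

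**Conclusion.** The point holds as a fault in a stated derivation rule for one secondary outcome. A month-9 non-smoker who smoked daily after month 3 can be scored as not relapsed while the same survey shows that smoking and fails the person on the primary outcome. Those missed altogether are people who relapsed after month 3 and re-quit, and people who relapsed earlier, re-quit and missed the 3-month survey. In each case they must also answer for the latest quit.

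Their number is unknown. The 25% to 75% above rests on assumed re-quit rates and is an upper bound on the share of month-9 non-smokers affected. Any effect on the arm comparison depends on re-quitting differing between arms, which the SAP gives no means to judge. The primary outcome has its own items and is untouched.

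**What to change.** In 4.1.2 vii, for participants not smoking at month 9, score relapse if they answer yes to the existing item **or** place their last daily smoking in any of the four bands from less than 1 week to 4–6 months. Keep the present rule as a sensitivity analysis. The extra condition works whether the outcome covers the time since month 3 or since discharge.

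Also state which window is meant. Carry month-3 relapse forward only if the window is since discharge, and note then that the month-3 rule has a lower threshold, since it also counts at-least-weekly smoking.

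Review the current-smoker route at the same time. A current daily smoker with no quit attempt of two days or more in the past six months is not scored as a relapse. Repairing the non-smoker route alone would leave the combined variable hard to interpret.

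The cost is one derivation rule and a sentence on the window, with no new data. There are two limits: the band item also counts daily spells shorter than a week, and it cannot separate a relapse that ended 7–9 months ago from smoking before admission.
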